1 PROTOCOL SUMMARY

No text is to be entered in this section; rather it should be included under the relevant subheadings below. It may be useful to complete this section after the relevant sections in the protocol have been completed.

[figure not shown]
1.1 SYNOPSIS

Title:	CTR radon DaCCoTA
Grant Number:	U54GM128729
Study Description:	The overall goal of this research is to compare the effectiveness of radon information delivered via the radon app vs. a traditional approach (printed brochure). The two methods will be compared on outcomes pertinent to the stages of individuals' responses to radon interventions.
Objectives* :	
Primary Objective: The primary objective of this research is to compare the effectiveness of radon information delivered via the radon app vs. a traditional approach (printed brochure) on behavioral outcomes, i.e., the rate at which individuals order free radon test kits and the rate at which they return them to the lab.
 
Secondary Objectives: The secondary objective of this research is to conduct a clinical trial to compare the effects of the radon app vs. brochures on increasing radon knowledge.

Endpoints* :	
Primary Endpoint:
 
1. Number of radon test kits requested by participants in the radon app and brochure conditions; and2. Number of radon test kits used and returned to the laboratory by participants in the two conditions. 
Secondary Endpoints:
 
Effectiveness of the radon app vs. brochure at 3 months re: changes in radon knowledge, as measured by the number of correct responses to a series of 20 true/false questions (e.g., "The EPA recommends that homes with 4 picocuries per liter (pCi/L) or more of radon should be fixed.").

Study Population:	Study participants are undergraduates in the Communication Department at the University of North Dakota. The principal eligibility criterion is that participants own a smartphone. The principal exclusion criterion is previous testing for radon within the past two years.
Phase* or Stage:	Phase II
Description of Sites/Facilities Enrolling Participants:	Enrolling participants was completed remotely via an online survey platform, Qualtrics.
Description of Study Intervention/Experimental Manipulation:	
An online experiment with two experimental conditions using a pretest-posttest design: the radon app condition vs. brochure condition. Participants in both experimental conditions will complete an online pre-exposure survey during the baseline phase of the study. Upon completion of the pre-exposure survey, participants assigned to the radon app condition will be asked to install the radon app on their smartphones and use the app for three months. App installation will be verified electronically via text message sent to the investigators. To make the informational content of the radon app and EPA brochures equivalent, the informational content in the app condition will be repurposed from EPA brochures used in the brochure condition. Participants in the radon app condition will have the opportunity to order a free radon test kit through the app at any time during the three-month period.
 
In contrast, individuals assigned to the brochure condition will receive three EPA brochures for the three-month period via postal mails. These brochures are (1) Basic radon facts (https://bit.ly/2S6ryFw); (2) A citizen's guide to radon (https://bit.ly/3l3FhcJ); and (3) Consumer's guide to radon reduction (https://bit.ly/3ibt83n). In each mailing, participants will receive a pre-addressed, pre-paid postcard to request a free radon test kit. The postcard will be addressed to a UND address so that we can track the number requested by participants in the brochure condition.

Study Duration* :	6 months.
Participant Duration:	3 months.

1.2 SCHEMA

Flow Diagram

1.3 SCHEDULE OF ACTIVITIES

The schedule of activities:

Category	Pre-screening (Pre-consent)	Visit 1 Day 1	Visit 2 Day 14 ±7	Visit 3 Day 28 ±7	Visit 4 Day 42 ±7	Visit 5 Day 56 ±7
EMR Review Eligibility	X					
Informed Consent		X				
Demographics and socioeconomic status		X				X
Baseline measures		X				
Outcome Evaluation: Radon knowledge		X				X
Outcome Evaluation: Ordering radon test kits						X
Outcome Evaluation: Utilizing radon test kits						X
Randomization		X				
Control & Experimental Interventions – The radon app vs. print brochures		X	X	X	X	
Adverse Events Reporting		X	X	X	X	X

2 INTRODUCTION

2.1 STUDY RATIONALE

Radon gas is a form of ionizing radiation that results from the natural decay of uranium present in rocks and soils. It is the largest cause of lung cancer after smoking and may contribute to death from other cancers, e.g., chronic lymphocytic leukemia^{1,2} and malignant melanoma.³ Radon causes more than 21,000 lung cancer deaths per year in the U.S.⁴ This number of deaths greatly exceeds those of other, more-publicized causes, e.g., drunk driving (17,400) and the number of homicides involving hand guns.⁵

Radon-related deaths result from a failure to test homes for radon. In part, this failure has a cognitive cause: the public's limited knowledge about radon. Additionally, among radon-knowledgeable individuals, the deaths have a behavioral cause; the failure of individuals to carry out a series of behaviors, including obtaining a radon test kit, using it, returning the kit to the lab, interpreting the results, and (if warranted), remediating their homes.

Many educational interventions concerning radon have been attempted. However, most have performed poorly when measured against real world outcomes like increases in radon testing. Importantly, most previous interventions have employed traditional forms of communication, such as printed brochures.⁶⁻⁹ Considerable evidence indicates that individuals may be more responsive to health information delivered via electronic media, e.g., the internet and smartphones.¹⁰ We recently designed a radon-education mobile application for smartphones ("the radon app") and pilot-tested it in a clinical trial with 96 individuals.¹¹ Findings from our pilot trial suggest that the radon app is a promising tool for promoting radon testing.¹¹

The overall goal of this research is to compare the effectiveness of radon information delivered via the radon app vs. a traditional approach (printed brochure). The two methods will be compared on outcomes pertinent to the stages of individuals' responses to radon interventions. These stages include radon knowledge, attitudes toward radon testing, ordering and using a test kit, and returning the kit to the lab for analysis.

2.2 BACKGROUND

In collaboration with a media services company (Triad Interactive Media, Greensboro, NC), we developed a radon app for smartphones.¹¹ Briefly, the app uses a framework in HTML5 and the open source Twitter API. Posts created by the app are cross-listed on Twitter. Once users log in via Twitter, they can view radon news and mobile-friendly informative content on radon repurposed from EPA brochures. Users also can access existing Tweets containing hashtags, e.g., #radon, #radonawareness, #radonmitigation, and #lungcancer. Individual users' activities on the radon app, along with their Twitter handle, are saved on Triad Interactive Media's server. Through the app, users could order a free radon test kit at any time.

We conducted a pilot clinical trial using this app. Ninety six (96) undergraduates at the University of North Dakota in Grand Forks, ND (UND) were assigned to use the radon app for one month and were tested on several aspects of radon knowledge and testing using a pretest-posttest design.¹¹ We have recently published our findings.¹¹ We found that the use of the radon app: (1) significantly improved individuals' radon knowledge and generated positive attitudes toward radon testing; (2) significantly increased self-efficacy (i.e., an individual's perceived capability to order a radon test kit and use it); (3) significantly increased response efficacy (i.e., an individual's evaluation of the effectiveness of radon testing in preventing radon exposure); and (4) resulted in 24% of study participants ordering a free radon test kit. However, only a small percentage of participants actually used the test kit they obtained (i.e., employed the test in their home and returned it to the lab; a total test completion rate of 9%).

In summary, our pilot trial demonstrated that the radon app improved radon knowledge, motivation to test, and stimulated requests for free test kits. However, our pilot trial had a key limitation: there was no control group (i.e., a group not exposed to the app). Our present research builds and improves upon these preliminary findings. To do so, we will include a control group that receives usual care (radon information communicated via EPA brochures).

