5 STUDY POPULATION

5.1 INCLUSION CRITERIA

In order to be eligible to participate in this study, an individual must meet all of the following criteria:

1. Reading the informed consent form
2. Age \geq 18
3. Own a smartphone

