5.2 EXCLUSION CRITERIA

An individual who meets any of the following criteria will be excluded from participation in this study:

1. Previous testing for radon within the past two years

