5.4 SCREEN FAILURES

Screen failures are defined as participants who consent to participate in this study but are not subsequently assigned to the study intervention or entered in the study. Individuals who do not meet the criteria for participation in this trial (screen failures) are automatically directed to the end of the pre-exposure survey.

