5.5 STRATEGIES FOR RECRUITMENT AND RETENTION

COMM 110 and 102 students were invited to participate in the study. In the communication department, students enrolled in COMM 102 are required to complete the 2-hour research participation requirement. The participation in both pre- and post-exposure surveys in each experiment would allow them to meet an hour of participation requirement. For COMM 110, students receive extra .5% in their final grade per an half-hour research participation, and they are allowed to earn up to extra 2% (i.e., 2-hour research participation), according to COMM 110's extra credit policy. The participation in both pre- and post-exposure surveys in each experiment would allow them to earn extra 1% for their final grade (i.e., one-hour research participation).

Approximately 200 students are enrolled in COMM 102 each semester, and about 600 students are enrolled in COMM 110 each semester. They are included in the Communication Department's SONA website, which is the research participation pool website run by the department. Once the study is available on SONA website, students receive an email from SONA, and if they agree to participate in the study, they will sign up for the study on SONA website. They will be able to sign up for a 30-minute time slot for the pre-exposure survey session. Those who complete the pre-exposure survey will receive the same recruitment email encouraging them to sign up for another 30-minute time slot for their post-exposure survey session. This method was deemed appropriate to reach this target study population because they were familiar with the SONA system overall and receiving study notification emails.

Participants who agree to be in the study will receive a pre-exposure online survey link. Once they click on the link, they will be asked to read the consent form first. Screening questions will appear on the next page. Those who met the eligibility criteria were then able to proceed with the questionnaire and randomized. Those who did not meet the eligibility criteria were directed to the end of the survey.

Half of the participants assigned to the radon app condition will be asked to provide their Twitter information. If participants don't have a Twitter ID, they will be asked to create a new one prior to

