6.3 MEASURES TO MINIMIZE BIAS: RANDOMIZATION AND BLINDING

Participants are assigned to either the radon app or brochure condition via the randomization function of Qualtrics. In other words, this trial will utilize the double-blind randomization.

There may be “contamination” of the exposures if participants assigned to the radon app share the app content with classmates assigned to the brochure condition. A consequence of this would be to dilute the effect of group exposure. Participants will be instructed not to share information with others about group assignment. Additionally, we will guard against this via a programming function that permits downloading of the radon app only by individuals assigned to the radon app condition.

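### Eligibility screens out recent radon testing but not earlier use of the app, so pilot users can enter either arm, including the brochure control

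*Combined protocol and SAP*

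**What the plan says.** Section 5.1 lists three inclusion criteria: having read the consent form, being 18 or older, and "Own a smartphone". Section 5.2 has a single exclusion, "Previous testing for radon within the past two years". Section 5.5 gives the consequence of passing: "Those who met the eligibility criteria were then able to proceed with the questionnaire and randomized".

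Section 2.2 says that 96 "undergraduates at the University of North Dakota in Grand Forks, ND (UND) were assigned to use the radon app for one month". It credits the app with better knowledge, with 24% of participants ordering a free kit, and with "a total test completion rate of 9" per cent. The present trial also recruits undergraduates at that university, from COMM 102 (about 200 students a semester) and COMM 110 (about 600).

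Section 6.3 discusses contamination, but only as sharing between classmates and as a block on downloads by students not assigned to the app. On assignment it says: "Participants are assigned to either the radon app or brochure condition via the randomization function of Qualtrics". No section says how a second sign-up by the same person would be handled. Section 9.3 analyses all randomised participants.

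**The concern.** The pilot is the protocol's own evidence that the app changes what this trial measures: knowledge and kit requests. Section 2.2 names the lack of an unexposed comparison group as the pilot's main limitation, and this trial is meant to supply one. A student who has already used the app does not provide that comparison if placed in the brochure arm, and has less left to gain if placed in the app arm. Either way that student contributes little to the contrast.

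Testing history is a weak stand-in for exposure, because few pilot users tested. Someone who learned the content, or who ordered a kit and left it unused, passes section 5.2.

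A smaller gap lies beside this one. Without a one-entry rule, a person entered twice has no defined arm under intent to treat, and the two records are not independent.

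**Working it through.** **Step 1. The plan's own power figure.** Section 9.2 states power of 0.8 to 0.9 for a 20-point difference with at least 100 per group. With n per arm, p̄ the mean of the two proportions and Δ = p1 − p2:

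power = Φ{[Δ − z·√(2p̄(1−p̄)/n)] / √[(p1(1−p1) + p2(1−p2))/n]}

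Alpha is not stated, so 0.05 is assumed. The arms are taken as equal (section 5.5 speaks of halves).

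| Brochure vs app | One-sided | Two-sided |
|---|---|---|
| 20% vs 40% | 0.930 | 0.876 |
| 24% vs 44% | 0.915 | 0.853 |
| 30% vs 50% | 0.898 | 0.828 |
| 40% vs 60% | 0.886 | 0.812 |

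The stated range is reproduced for mid-range rates.

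**Step 2. How many pilot users section 5.2 lets through.** If the 9% is a share of all 96, then 96 × 0.91 = 87.4, so about 87 did not complete a test. About 96 × (0.24 − 0.09) = 14.4, or 14 people, ordered a kit and did not use it. The 87 counts people who pass the testing criterion, not people who would enrol. Anyone among them who tested by another route within two years would still be excluded.

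**Step 3. Dilution.** Let f be the share of both arms with earlier app exposure. Assume that the app-brochure difference among them is zero. The overall difference is then 20 × (1 − f) points, so each 5% exposed removes 1 point. The table applies the Step 1 formula, one-sided, holding the brochure rate fixed. The documents give no brochure rate, so a range is shown.

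| f | Difference | Brochure 4% | Brochure 24% | Brochure 40% |
|---|---|---|---|---|
| 0 | 20 points | 0.994 | 0.915 | 0.886 |
| 5% | 19 points | 0.991 | 0.890 | 0.856 |
| 10% | 18 points | 0.987 | 0.860 | 0.820 |
| 20% | 16 points | 0.971 | 0.786 | 0.735 |

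A two-sided test at 0.05 with a 24% brochure rate goes from 0.853 (f = 0) to 0.777 (f = 10%).

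**Step 4. What share is plausible.** The pool is about 200 + 600 = 800 students a semester. If pilot users volunteer at the same rate as others, f = 5% needs 0.05 × 800 = 40 of them in the pool and f = 10% needs 80. All 87 would give 87/800 = 10.9%. A share of 20% would require pilot users to be over-represented among volunteers. Nothing in the documents says how many are in these courses.

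**Step 5. Duplicate entry.** Section 8.1 records which email address went to which condition, and when. That is enough to find a repeat under the same address and to identify the first assignment. What is missing is the instruction to look and the rule to apply.

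**The case against.** The strongest reply is that the exposed group is probably small. Pilot users must now be in COMM 102 or 110, and section 2.2 does not say which courses supplied the pilot. At 5% exposed, one-sided power stays above 0.8 at every rate shown. Randomisation spreads these students across both arms. Baseline knowledge is measured, and the knowledge endpoint is a change. A former user who already received a kit might not order again, so a previously exposed control participant need not raise the brochure rate. All of this stands. It limits the size of the problem but does not close the gap, and it is why the figures above are illustrations.

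A reader might go further and infer that students can reopen the survey link to choose their arm or change a screening answer, and that this breaks the randomisation. The documents do not support that. They are silent on link reuse and on SONA or Qualtrics response limits. Section 5.4 says only that screen failures "are automatically directed to the end of the pre-exposure survey". The sequence is also inconsistent: section 5.5 puts the Twitter and installation steps before the survey is completed, sections 1.1, 4.1 and 6.1.1 put installation after it, and section 8.1 has baseline questions answered before assignment. Nothing says that a second entry earns a second payment, and section 8.1 keeps a dated record of assignments. Repeat entry is unaddressed; it is not shown to happen. Nor do the documents justify forbidding all re-screening.

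**Conclusion.** The point holds as a gap in eligibility. Former users of this app at the same university are not excluded, and about 87 of the 96 would pass the testing criterion. The expected effect is dilution and higher baseline knowledge, not systematic bias. Under the assumptions in the working (100 per arm, one-sided 0.05, no arm difference among the exposed), 10% exposure costs about 5 to 7 points of power at brochure rates of 24% and 40%, and under 1 point at 4%. The real share is unknown and may be close to zero. This is worth correcting because it is cheap, not because the comparison is otherwise unsound. The lack of a one-entry rule is secondary and needs a stated procedure.

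**What to change.** Add an exclusion to section 5.2 for anyone who took part in the radon app pilot or has previously used the radon app, and put the question on the screening page. The cost is one item and a few students made ineligible, against a pool of about 800 a semester and a target of 2 × 100 = 200.

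For repeat entry, make three short additions:

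- Set the pre-exposure survey to accept one response per SONA ID. If SONA or Qualtrics already does this, say so in section 5.5.
- Check the email-to-condition record described in section 8.1 for duplicates.
- State in section 9.3 that a person's first assignment stands for the intent-to-treat analysis.

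These cost a survey setting, one data check and a sentence.

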2.3 RISK/BENEFIT ASSESSMENT

2.3.1 KNOWN POTENTIAL RISKS

The research presents no more than minimal risk, as participants would use a smartphone as they would do normally or receive postal mails as part of experimental interventions, as indicated in a similar previous study.¹¹ In other words, there are neither immediate risks nor long-term risks.

2.3.2 KNOWN POTENTIAL BENEFITS

This research would provide a better understanding of how to increase the public's awareness of the radon issue. The immediate potential benefits would include increased awareness of the health threat posed by radon, as indicated in our similar previous study.¹¹ The long-term potential benefits would include the lower risks of developing lung cancer due to radon exposure.

2.3.3 ASSESSMENT OF POTENTIAL RISKS AND BENEFITS

There are no risks in participating in this research beyond those experienced in everyday life. Yet, just in case participants feel any psychological/emotional distress or discomfort, they will be instructed to withdraw from the study at any time without losing the course points assigned by their instructor. Also, they may meet the one-hour research requirement for their COMM 102 class or receive one extra credit for their COMM 110 class by completing an alternative task, which is to read an article related to this research and prepare a two-page reaction to it. Given the little to no risks and potential immediate and long-term benefits, the value of the information to be gained outweighs the risks of participation in the study.

3 OBJECTIVES AND ENDPOINTS

OBJECTIVES	ENDPOINTS	JUSTIFICATION FOR ENDPOINTS	PUTATIVE MECHANISMS OF ACTION

PRIMARY: The primary objective of this research is to compare the effectiveness of radon information delivered via the radon app vs. a traditional approach (printed brochure) on behavioral outcomes, i.e., the rate at which individuals order free radon test kits and the rate at which they return them to the lab.
	
1. Number of radon test kits requested by participants in the radon app and brochure conditions; and
 
2. Number of radon test kits used and returned to the laboratory by participants in the two conditions.
	
Each measure is the dependent variables to test the primary objective.
	

SECONDARY: The secondary objective of this research is to conduct a clinical trial to compare the effects of the radon app vs. brochures on increasing radon knowledge.
	
Effectiveness of the radon app vs. brochure at 3 months re: changes in radon knowledge, as measured by the number of correct responses to a series of 20 true/false questions (e.g., “The EPA recommends that homes with 4 picocuries per liter (pCi/L) or more of radon should be fixed.”).
	
The radon knowledge variable is a key dependent variable to test the secondary objective. The radon knowledge variable may potentially serve as the mediator of the effects of the interventions on two measures identified as primary endpoints.
	

4 STUDY DESIGN

4.1 OVERALL DESIGN

The project begins by comparing the role of the radon app vs. brochures on the percentage of participants that request free test kits and use and return them to the laboratory for analysis and improving knowledge about radon (Phase II).

Experimental design. We designed an online experiment with two experimental conditions—the radon app condition vs. brochure condition—using a pretest-posttest design. Study participants are undergraduates in the Communication Department at UND, indicating that this is a single-site trial. The principal eligibility criterion is that participants own a smartphone. The principal exclusion criterion is previous testing for radon within the past two years.

We consider UND undergraduates to be an appropriate population to test the app for several reasons: (1) ND has the highest residential radon levels in the U.S.²; (2) Our recent review of radon knowledge indicated that most individuals less than 30 years old do not know what radon is¹²; and (3) The age of many undergraduate students is similar to that of first time home-buyers in the U.S.¹³ We will assign recruited participants randomly to one of the two experimental conditions: app use and brochures.

Participants in both experimental conditions will complete an online pre-exposure survey during the baseline phase of the study. Upon completion of the pre-exposure survey, participants assigned to **the radon app condition** will be asked to install the radon app on their smartphones and use the app for three months. App installation will be verified electronically via text message sent to the investigators. To make the informational content of the radon app and EPA brochures equivalent, the informational content in the app condition will be repurposed from EPA brochures used in the brochure condition. Participants in the radon app condition will have the opportunity to order a free radon test kit through the app at any time during the three-month period.

In contrast, individuals assigned to **the brochure condition** receive three EPA brochures for the three-month period via postal mails. These brochures are (1) Basic radon facts (<https://bit.ly/2S6ryFw>); (2) A citizen's guide to radon (<https://bit.ly/3l3FhcJ>); and (3) Consumer's guide to radon reduction (<https://bit.ly/3ibt83n>). In each mailing, participants will receive a pre-addressed, pre-paid postcard to request a free radon test kit. The postcard will be addressed to a UND address so that we can track the number requested by participants in the brochure condition.

Outcome measures. Participants in both groups will complete the pre-exposure online survey at the beginning of the study and a post-exposure online survey at the three-month time point. This knowledge-based survey is similar to one we have used previously.¹¹ The primary endpoints used to compare the two approaches are:

1. Number of radon test kits requested by participants in the radon app and brochure conditions;
2. Number of radon test kits used and returned to the laboratory by participants in the two conditions.

3. Effectiveness of the radon app vs. brochure¹¹ at 3 months re: changes in: radon knowledge, as measured by the number of correct responses to a series of 20 true/false questions (e.g., “The EPA recommends that homes with 4 picocuries per liter (pCi/L) or more of radon should be fixed.”).

